9.6 Sample size calculation

All Parts:

The stopping rules as defined in [Section 5.5.10](#) are designed to ensure that a CFZ533 treatment arm will be stopped if there is a high probability (>90%) that the true tBPAR rate is greater than 20%.

[Figure 9-1](#) indicates the probability of stopping for an arm for various true tBPAR rates and shows that the stopping rules ensure that the chance of stopping an arm are sufficiently high for true high tBPAR rates while remaining appropriately low when the true rates are low.

Figure 9-1 Probability of stopping a cohort for various true tBPAR rates

Part 2

Operating characteristics

The sample size justification for Part 2 considers the probability of progressing further development or not progressing based on the planned safety stopping rules and the success criteria for the planned sample size.

The safety stopping rules (see [Section 5.5.10](#)) ensure that the study will not continue if:

$\Pr(\theta_{CFZ533} > 0.20 \mid \text{data}) > 90\%$

[figure not shown]
The success criteria (see [Section 9.4.2](#)) are met if:

$$\Pr(\theta_{CFZ533} - \theta_{SoC} < 0.20 \mid \text{data}) > 60\%.$$

[Figure 9-2](#) shows the chances of continuing development (i.e., of not meeting the safety stopping rules and meeting the success criteria) on the y-axis for a range of true values of the tBPAR rate for CFZ533 (x-axis) and for three possible control rates (blue and grey curves). The probability of moving is high when CFZ533 has a low true tBPAR rate and is comparable to control. For example, if the true CFZ533 rate is less than 20% and the true control rate is around 10%, there is a greater than 80% probability of progressing to Part 3.

Conversely, when the true tBPAR rate for CFZ533 is high, the probability of not continuing is high. For example, there is an approximately 80% probability of not progressing when the true CFZ533 rate is more than 25% greater than the true control rate.

Figure 9-2 Probability of progressing for different true values of tBPAR for CFZ533 and control

These calculations assume that the primary efficacy variable, rate of tBPAR, follows a binomial distribution. The prior distribution for the control tBPAR rate, Beta(1, 13), is estimated from a Bayesian meta-analysis of tBPAR rates from four previous studies using a control treatment similar to the one used in this study. The four studies were selected from the studies used in a previous Novartis generated meta-analysis studies and are summarized in Table 9-1.

Table 9-1 Summary of historical control data

Study	Treatment	Number of patients with tBPAR	Total number of patients	tBPAR rate
1 - Vincenti et al 2007	B+Tac+MMF+CS	24	346	0.069
2 - Silva et al 2007	B+Tac XL+MMF+CS	17	214	0.079
3 - Silva et al 2007	B+Tac+MMF+CS	8	212	0.038
4 - Scholten et al 2006	B+Tac+ MMF(0.5g)+CS	4	63	0.063

B=basiliximab

Prediction of the control rate for a future trial resulting from the Bayesian meta-analysis is shown in Figure 9-3.

Figure 9-3 Results of Bayesian meta-analysis prediction

[figure not shown]

Figure 9-3 shows estimates of response rate and 95% credible intervals for each study based on study data alone (dashed lines) and from the meta-analysis (solid lines). The overall prediction for response rate in a future study is shown in red together with the mean and 95% credible interval from the posterior distributions and n^* , the prior number of observations that these data would contribute to a future analysis.

To allow for a simple randomization ratio for allocation of patients to treatment groups, it was decided to reduce the control arm to 15 patients, compared to 30 for the CFZ533 arms. Thus a prior beta distribution of Beta (1, 13) was chosen, which has a mean value of 7 with 95% CI (0.2, 24) and an approximate weight of 14 patients.

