3.1.2 All cohorts

Before any study-related evaluations are performed, the patient must give written informed consent. Once consent is obtained, pre-transplant screening and baseline assessments will occur to determine the patient's eligibility to participate in the study starting up to 28 days prior to transplantation. If the screening, baseline and study Day 1 visits occur in close proximity of each other (i.e., within a 12 hour timespan), certain repeated assessments may be omitted, as noted in the [Assessment schedule](#). Data collection from assessments performed at the clinical site as part of medical standard of care but prior ICF sign-off is acceptable in order to confirm patient eligibility for patients receiving an organ from a deceased donor, if assessed shortly before transplantation (i.e within 24h – matching the baseline window of Day -1 to Day 1) and in-line with inclusion and exclusion criteria.

Day 1 is defined as the day of randomization/enrollment and transplantation. This protocol defines 7 days to a week and 4 weeks (or 28 days) to a Study Month. For example, Week 2 is considered to start on Day 8 and Study Month 2 is considered to start on Week 5/Day 29. Randomization/enrollment should occur within 24 hours pre-transplant and drug administration will begin after randomization/enrollment. If CFZ533 is to be administered, the first dose of CFZ533 will be administered IV pre-transplant or intra-operatively, and must be completed by the time of unclamping. Other study drugs must be started within 24 hours post-transplant or according to local practice.

Patients who are randomized/enrolled but not transplanted will be replaced. All randomized/enrolled subjects are expected to continue in the study up to Month 6 (Part 1) or Month 12 (Part 2) regardless of being on or off randomized/assigned treatment. All subjects will be followed-up for safety (e.g., SAEs) for approximately three months after their last dose of CFZ533 or 2 months after the EoS visit for patients on SoC treatment.

[figure not shown]
Any treatment arm in which the rejection rate fulfills the *a priori* defined stopping rules (see [Section 5.5.10](#)) will be immediately discontinued at any time during the study.

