5.4 Treatment blinding

This is an open-label, exploratory study and it is not planned to blind patients or site staff to treatment. In Part 1 since there is just one treatment arm, it will be known to the whole Clinical Trial Team that the subjects all received 3mg/kg CFZ533. In Part 2, core Clinical Trial Team members will be unblinded to continuously review safety and clinical data and evaluate the stopping rules.

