5.5.10 Discontinuation of study treatment and premature subject withdrawal

Study “Stopping rules”

The following stopping rules based on potential toxicities will serve as the basis for placing the study on hold. Although the stopping criteria do not incorporate an absolute requirement for causality, the potential relationship between an AE and CFZ533 will be evaluated carefully on a case-by-case basis between the Sponsor and the Investigator. Following a review of the AE(s), a decision to permanently discontinue enrollment or re-initiate dosing will be made by the DMC.

- Two (2) or more patients presenting with PTLD or PML

In addition, specific stopping rules for the incidence of tBPAR will be applied. These rules are designed to ensure that a CFZ533 treatment arm will be stopped if there is high probability (>90%) that the true tBPAR rate is greater than 20%. Corporate Confidential Information

Corporate Confidential Information

In addition to the automatic hold criteria and tBPAR criteria presented above, the DMC will review safety data regularly as outlined in their charter (see [Section 8.4](#)) during quarterly and *ad hoc* meetings. The DMC can recommend stopping a specific study arm(s) or the entire trial if significant changes or effects that, in their collective opinion, are deemed unsafe or unethical to continue administering CFZ533.

Discontinuation of study regimen

The Dosage Administration Records for CFZ533 (all parts), MMF and Tac (Part 1 only) and Concomitant Medication eCRF for MMF and Tac (Part 2) will be used to record if a subject has permanently discontinued study treatment and why.

Possible reasons for study treatment discontinuation are:

- Adverse Event
- Lack of Efficacy
- Technical problem during transplant surgery
- Subject/Guardian Decision
- Lost to follow-up
- Death
- Graft Loss

The Investigator should discontinue a subject from their randomized treatment regimen if, on balance, he/she believes that continuation would be detrimental to the subject's well-being.

Subjects who become pregnant while taking study medication must be discontinued from study medication and from the study, such pregnancies should be reported as SAEs to Novartis DSE and entered as AEs in the eCRF, the reason for discontinuation of study medication should be recorded as AE and reason for discontinuation from study is pregnancy (see next section below).

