- Females of reproductive potential taking CellCept® must receive contraceptive counseling and use acceptable contraception (see [Table 14-1](#) for Acceptable Contraception Methods). Patients must use acceptable birth control during entire CellCept® therapy, and for 6 weeks after stopping CellCept®, unless the patient chooses abstinence (she chooses to avoid heterosexual intercourse completely).
- Patients should be aware that CellCept® reduces blood levels of the hormones in the oral contraceptive pill and could theoretically reduce its effectiveness.

Table 14-1 Acceptable Contraception Methods for Females of Reproductive Potential*

Option 1 Methods to Use Alone	
 • Intrauterine device (IUD) • Tubal sterilization • Patient's partner had a vasectomy 		
OR			
Option 2 Choose One Hormonal Method AND One Barrier Method	Hormone Methods choose 1		Barrier Methods choose 1
	Estrogen and Progesterone 
 • Oral contraceptive pill • Transdermal patch • Vaginal ring Progesterone-only 
 • Injection • Implant 	AND	
 • Diaphragm with spermicide • Cervical cap with spermicide • Contraceptive sponge • Male condom • Female condom
OR			
Option 3 Choose One Barrier Method From Each Column (must choose two methods)	Barrier Methods choose 1		Barrier Methods choose 1
	
 • Diaphragm with spermicide • Cervical cap with spermicide • Contraceptive sponge 	AND	
 • Male condom • Female condom

*Females of reproductive potential include girls who have entered puberty and all women who have a uterus and have not passed through menopause.

15 Appendix 3: Stopping rules

Transition rules are based on both efficacy and safety results from Part 2. In Part 2, treatment arms are as follows:

- A: CFZ533 10mg/kg (IV);
- B is Control

Then the rules are as follows:

- If A is terminated for any reason, then STOP the study.

The following rules are for terminating treatment group(s) from Part 2:

For safety:

- Terminate the treatment group if there are two (2) or more patients presenting with PTLD or PML in that group.
- For toxicities, AEs / infections, and causalities, case-by-case review is needed to determine any treatment group(s) should be terminated.

For efficacy (based on the number of patients with tBPAR):

- If no tBPAR for SoC, then any group with tBPAR ≥ 7 will be terminated.

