1.4.3 Study “stopping” rules

The following stopping rules based on potential toxicities will serve as the basis for placing the study on hold. Although the stopping criteria do not incorporate an absolute requirement for causality, the potential relationship between an AE and CFZ533 will be evaluated carefully on a case-by-case basis between the Sponsor and the Investigator. Following a review of the AE(s), a decision to permanently discontinue enrollment or re-initiate CFZ533 dosing will be made by the DMC.

- Two (2) or more patients presenting with post-transplant lymphoproliferative disease or progressive multifocal leukoencephalopathy in the CFZ533 treatment arm.

In addition, specific stopping rules for the incidence of tBPAR will be applied. These rules are designed to ensure that an arm will be stopped if there is high probability ($> 90\%$) that the true tBPAR rate is greater than 20%. Based on this stopping rule, the maximum number of patients with tBPAR for various different illustrative sample sizes would be as follows:

Table 1-1 Study stopping rules for tBPAR

Total number of patients (N)	Number of patients with tBPAR that would lead to stopping the treatment arm (n)	Observed tBPAR rate (n/N)
3	2	0.67
4	2	0.50
5	3	0.60
6	3	0.50
7	3	0.43
8	4	0.50
9	4	0.44
10	4	0.40
11	5	0.45
12	5	0.42
13	5	0.38
14	5	0.36
15	6	0.40
16	6	0.38
17	6	0.35
18	6	0.33
19	7	0.37
20	7	0.35
21	7	0.33
22	7	0.32
23	8	0.35
24	8	0.33
25	8	0.32
26	8	0.319
27	9	0.33
28	9	0.32
29	9	0.31
30	9	0.30

In addition to the automatic hold criteria and tBPAR criteria presented above, the DMC will review safety data regularly as outlined in their charter during quarterly and ad hoc meetings. The DMC can recommend stopping a specific study arm(s) or the entire trial if significant changes or effects that, in their collective opinion, are deemed unsafe or unethical to continue administering CFZ533.

2 First interpretable results (FIR)

First interpretable results (FIR) will be provided for this trial.
Corporate Confidential Information

Corporate Confidential Information

4 Statistical methods: Analysis sets

For patients for which the actual treatment received does not match the randomized treatment, the treatment actually received will be used for the analysis.

The Full Analysis Set will include all patients that received at least one dose of study drug and who were transplanted.

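### The >80% chance of progressing in Protocol 9.6 fits one evaluation at N=30; with the ongoing stopping-rule evaluation the protocol describes, the range of true rates it covers can be shorter, and the looks are not stated

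*Protocol*

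**What the plan says.** Protocol 9.6 justifies 30 CFZ533 and 15 control patients by the probability of continuing development, defined as the chance "of not meeting the safety stopping rules and meeting the success criteria". The stopping rule is Pr(θ_CFZ533 > 0.20 | data) > 90%. Success is Pr(θ_CFZ533 − θ_SoC < 0.20 | data) > 60%. The worked example drawn from Figure 9-2 is that "if the true CFZ533 rate is less than 20% and the true control rate is around 10%, there is a greater than 80% probability" that the trial progresses. A companion sentence puts the chance of not progressing at about 80% when the CFZ533 rate exceeds control by more than 25% (read here as percentage points). Figure 9-2 covers three control rates, but the companion sentence names none of them.

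Other sections describe when the stopping rule is applied:

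- Protocol 3.1.2: an arm that fulfils the rule "will be immediately discontinued at any time during the study".
- Protocol 5.4, on Part 2: "core Clinical Trial Team members will be unblinded to continuously review safety and clinical data and evaluate the stopping rules".
- SAP 1.4.3, Table 1-1: a boundary for every N from 3 to 30, introduced with the words "the maximum number of patients with tBPAR for various different illustrative sample sizes would be as follows".
- Protocol Appendix 3: "The following rules are for terminating treatment group(s) from Part 2", followed by tBPAR counts of at least 7, 8 or 9 when control has 0, 1 or more than 1 event.

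**The concern.** The probability of progressing depends on how often the stopping rule is evaluated. An arm with a true rate in the upper teens can cross an early boundary by chance and be stopped, although its final count would have met the success criterion. A calculation that applies the rule only at N=30 leaves those paths in. Section 9.6 does not say how many evaluations its figure assumes, while Sections 3.1.2 and 5.4 describe ongoing evaluation. If the figure rests on one final look, it overstates the chance of progressing exactly where the decision is most sensitive, and this sentence and Figure 9-2 are the argument for 30/15.

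**Working it through.** **Inputs.** Binomial tBPAR counts with 30 and 15 patients, and the two criteria (Protocol 9.6). Priors Beta(1/3, 1/3) for CFZ533 and Beta(1, 13) for control (Protocol 9.4.2). Boundaries by N (SAP Table 1-1). Below, r is the number of CFZ533 events and s the number of control events.

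**Step 1: stopping boundary.** The posterior after N patients is Beta(1/3 + r, 1/3 + N − r). At N=30, Pr(θ > 0.20) is 0.812 for r=8 and 0.904 for r=9, so the arm stops at 9. The same formula reproduces all 28 rows of Table 1-1.

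**Step 2: success region.** The control posterior is Beta(1 + s, 28 − s). Integrating numerically, Pr(difference < 0.20) is:

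- s=0: 0.656 at r=6 and 0.495 at r=7
- s=1: 0.642 at r=7 and 0.496 at r=8
- s=2: 0.633 at r=8 and 0.498 at r=9

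Success therefore allows r up to 6 + s.

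**Step 3: the plan's figure, with one look at N=30.** Progress requires r ≤ 6, 7 or 8 for s = 0, 1 or at least 2. With control at 10%, these s values have probabilities 0.2059, 0.3432 and 0.4510.

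- True rate 19%: 0.2059 × 0.6603 + 0.3432 × 0.8032 + 0.4510 × 0.8996 = 0.817
- True rate 20%: 0.2059 × 0.6070 + 0.3432 × 0.7608 + 0.4510 × 0.8713 = 0.779

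The probability reaches 80% at a true rate of 19.5%. The stated figure is reproduced to rounding.

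**Step 4: repeated looks.** Carry the distribution of r forward one patient at a time, v(r) ← v(r)(1 − p) + v(r − 1)p. At each look, remove all paths at or above the Table 1-1 boundary. Then combine with Binomial(15, 0.10) over the success region.

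| Looks (N) | P(progress) at 15% | at 19% | at 20% | true rate where it falls to 80% |
|---|---|---|---|---|
| success criterion alone | 93.6% | 82.9% | 79.4% | 19.8% |
| 30 | 93.2% | 81.7% | 77.9% | 19.5% |
| one of 27 to 29, and 30 | 93.2% | 81.7% | 77.9% | 19.5% |
| 15, 30 | 92.6% | 80.7% | 76.7% | 19.2% |
| 8, 15, 23, 30 | 91.5% | 79.0% | 75.0% | 18.7% |
| 10, 20, 30 | 89.8% | 76.5% | 72.4% | 18.1% |
| every 5 | 88.7% | 75.0% | 70.8% | 17.7% |
| every N from 3, no lag | 80.5% | 65.5% | 61.3% | 15.2% |

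Looks at 27 to 29 change nothing because the boundary there is already 9, so any path they stop is also stopped at 30. An added look can only remove progressing paths, which makes 19.8% the ceiling for any schedule at control 10%.

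**Step 5: control rate.** For control 8 / 12%, the range ends at 18.9 / 20.0% with one look, 18.6 / 19.6% for looks at 15 and 30, and 17.7 / 18.4% for 10, 20 and 30.

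**Step 6: event lag (assumptions, not in the documents).** Take accrual of all 45 patients spread evenly over 6 to 24 months, events uniform over 3 months, the rule checked at each event, and N equal to CFZ533 patients enrolled so far. P(progress) at 20% is then 76.7% (6 months) to 68.8% (24 months), and the range ends between about 19% and 17%.

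**Step 7: Appendix 3.** Over all 31 × 16 = 496 final outcomes, staying below 7/8/9 is identical to meeting success and not being stopped at N=30. At smaller N the rules differ: Table 1-1 can stop an arm with 2 to 6 events at N of 18 or fewer, and Appendix 3 never stops below 7. Applied after every patient (2:1 blocks, no lag), Appendix 3 gives 80.2 to 80.9% at a true rate of 19%, and the range ends at 19.0 to 19.2%.

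**Step 8: companion figure.** P(not progressing) at control + 25 points, for control 5 / 7 / 10%, is 74.3 / 77.2 / 80.9% on the criterion alone and 77.6 / 81.5 / 87.0% with looks at 10, 20 and 30. About 80% fits either reading.

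**The case against.** Section 9.6 contains no arithmetic slip. It prints its stopping rule, refers to the planned sample size, and says around 10%; on a single final look the sentence is right to rounding. The input that decides the size of the shortfall, the look schedule, cannot be seen: text after the tBPAR rule in Section 5.5.10 is redacted, Table 5-1 is listed but not visible, and Figures 9-1 and 9-2 are not shown. The absence of a schedule therefore cannot be held against the plan, and Figure 9-2 cannot be shown to omit repeated looks. Some repeated schedules cost nothing (27 and 30) or little (15 and 30; Appendix 3). A looser reading of the control rate also helps: at 12%, a single look reaches 20.0%. The SAP calls its sample sizes illustrative, and the 15% limit needs a look after every patient with no event lag.

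All of this stands, and it limits the size of the point. It does not remove the mismatch. Sections 3.1.2 and 5.4 describe ongoing evaluation, Section 9.6 counts avoiding the stopping rule as part of progressing, and no hidden schedule can lift the range at control 10% above 19.8%.

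**Conclusion.** The >80% statement describes a single evaluation at N=30. Under the ongoing evaluation the protocol describes, the >80% range at control 10% ends somewhere from 19.5% (only late looks added) to 17.7% (every five patients), with about 15% as an unrealistic lower limit. At a true rate of 20%, the probability of progressing is 77.9% down to 70.8% over the same schedules. This rests on the stated priors, binomial sampling, 30/15 patients, the Table 1-1 boundaries and no event lag.

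A reader might infer more than the documents support:

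- That the range always ends at 19% or lower. It does not; late looks leave it at 19.5%.
- That 15% should replace 20%. It should not, because zero lag with per-patient looks is not a realistic schedule.
- That the companion figure is wrong. This is not shown; it only lacks its control rate.
- That the sample size is inadequate. P(progress) at a true rate of 15% stays at 89% or more for every schedule in the table except the zero-lag limit.

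The consequence is modest: an optimistic operating characteristic for arms with a true rate in the upper teens, and two stopping-count rules in print that agree with the success decision only on final data.

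**What to change.** - Rerun the Figure 9-2 operating characteristics with the stopping rule applied at the looks the trial will use. State those looks in Section 9.6, or cross-refer to them if they are in redacted text.
- Restate the range of true CFZ533 rates for which the probability of progressing exceeds 80% at control 10%. Do not use the zero-lag value as the replacement.
- Give the control rate that belongs to the companion 80% figure.
- Reconcile the Section 5.5.10 / SAP Table 1-1 rule with the Appendix 3 counts, and say how each enters the calculation.

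The cost is one rerun, one figure, two restated sentences and a reconciling note. The stated range becomes slightly less favourable. Boundaries, success criterion and sample size stay as they are.

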9.7 Power for analysis of key secondary variables

Table 9-2 provides 80% and 95% CIs for between-treatment difference (CFZ533-control regimen) based on an assumed SD and difference for eGFR_{MDRD}. Since this is an exploratory phase 2 trial, evidence of renal benefit will be based on a 80% CI. In line with the SYMPHONY study (Ekberg et al 2007), a difference of 6.5 mL/min/1.73m² between treatment regimens is considered to be the lower limit of clinically relevant benefit.

Table 9-2 Two-sided 80 and 95 percent example CIs for between-treatment difference (CFZ533-Control regimen) of calculated eGFR (MDRD), assuming dropout rate = 30 percent (n = 53/group)

Observed Standard Deviation	Observed difference in eGFR _{MDRD} CFZ533 – control	80% CI	95% CI
16	4.0	(-0.0, 8.0)	(-2.2, 10.2)
	5.0	(1.0, 9.0)	(-1.2, 11.2)
	6.0	(2.0, 10.0)	(-0.2, 12.2)
	7.0	(3.0, 11.0)	(0.8, 13.2)
	8.0	(4.0, 12.0)	(1.8, 14.2)
18	4.0	(-0.5, 8.5)	(-3.0, 11.0)
	5.0	(0.5, 9.5)	(-2.0, 12.0)
	6.0	(1.5, 10.5)	(-1.0, 13.0)
	7.0	(2.5, 11.5)	(0.0, 14.0)
	8.0	(3.5, 12.5)	(1.0, 15.0)
20	4.0	(-1.0, 9.0)	(-3.7, 11.7)
	5.0	(-0.0, 10.0)	(-2.7, 12.7)
	6.0	(1.0, 11.0)	(-1.7, 13.7)
	7.0	(2.0, 12.0)	(-0.7, 14.7)
	8.0	(3.0, 13.0)	(0.3, 15.7)

10 Ethical considerations

